2.6.2 Statistical hypothesis, model, and method of analysis

Subject-level assessments

Subject-level PPV, NPV, accuracy will be summarized with corresponding exact 95% CI.

Region-level assessments

Region-level sensitivity, specificity, PPV, NPV, accuracy will be summarized respectively with corresponding exact 95% CI by regions.

Region consists of liver, pancreas, gastrointestinal, lymph nodes and others.

Number of lesions detected by imaging

Descriptive statistics for number of lesions will be provided by region-level and subject-level.

Regarding [⁶⁸Ga]Ga-DOTA-TATE PET/CT imaging, descriptive statistics of number of lesions for each of the 3 central reader , and 3 readers' mean number of lesions will be presented.

Regarding CIM, descriptive statistics of number of lesions detected by [¹¹¹In]In-Pentetreotide SPECT/CT and High Resolution CT with contrast (or MRI if CT with contrast is medically contraindicated) will be presented respectively.

Listing for number of lesions will be provided.

Impact on treatment decision

The number (%) of participants for intended treatment plan at pre and post [⁶⁸Ga]Ga-DOTA-TATE PET/CT imaging and the number (%) of participants for whom the intended treatment plan has changed and for whom it has not changed will be summarized. The number (%) of

participants will also be summarized for each combination of transition of intended treatment plan.

Listing for intended treatment plan will be provided.

Inter-reader variability

Each central read subject-level result (positive or negative), inter-reader variability (%) and its 95% CI will be presented.

Inter-reader variability will be assessed by Fleiss' Kappa (κ_1) statistic ([Fleiss 1971](#)). Refer to [Section 5.4.2](#) for details on Fleiss' Kappa.

An additional table will be presented to show the distribution of agreements with the number (%) of scans agreed by two readers and the number (%) of scans agreed by all three readers.

If one of the central readers is changed during the study and the total amount of its read is more than 30% of the total number of participants who have evaluable [⁶⁸Ga]Ga-DOTA-TATE PET/CT, inter-reader variability for each combination (before the change and after the change) and its normality 95% CI will be presented additionally. The distribution of agreements with the number (%) of scans agreed by two readers and the number (%) of scans agreed by all three readers will be also presented for each combination.

Lesion-level concordance rate for SSTR

For patients who have histopathology assessments, total number of patients, result of local histopathology (lesion-level positive or negative), result of [⁶⁸Ga]Ga-DOTA-TATE PET/CT imaging by local read (lesion-level positive or negative), numbers (%) of lesion-level concordance and its exact 95% CI will be presented.

All local histopathology assessments will be listed.

2.6.3 Handling of intercurrent events

Not applicable.

2.6.4 Handling of missing values not related to intercurrent event

This is a diagnostic study and secondary endpoints (subject-level PPV/ NPV/ accuracy and region-level sensitivity/ specificity/ PPV/ NPV/ accuracy) are calculated on the basis of [⁶⁸Ga]Ga-DOTA-TATE PET/CT imaging and CIM assessments. The secondary analyses will be conducted for the EFF and missing data related to these endpoints will not occur in the population.

For other secondary endpoints, missing data will not be imputed.

2.6.5 Sensitivity analyses

No sensitivity analyses are planned for the secondary endpoints.

2.6.6 Supplementary analyses

No supplementary analyses are planned for the secondary endpoints.

2.7 Safety analyses

For all safety analyses, the Safety Set will be used. All listings and tables will be presented by group (i.e. Patients with confirmed/suspected NENs and HVs).

Safety summaries (tables, figures) include only data from the on-treatment period with the exception of baseline data which will also be summarized where appropriate (e.g. change from baseline summaries).

2.7.1 Adverse events (AEs)

Adverse events are coded using MedDRA terminology. The latest MedDRA version used for reporting will be specified in the CSR and as a footnote in the applicable tables/listings. AEs will be assessed according to the Common Terminology Criteria for Adverse Events (CTCAE) version 5.0.

AE summaries will include all AEs that started or worsened during the on-treatment period, the **treatment-emergent** AEs. All AEs collected in the 'AE' eCRF page will be listed along with the information collected on those AEs e.g. AE relationship to study drug, AE outcome etc. AEs with start date outside of on-treatment period will be flagged in the listings.

AEs will be summarized by number (%) of subjects having at least one AE, having at least one AE in each primary SOC and for each PT using MedDRA coding. A subject with multiple occurrences of an AE will be counted only once in the respective AE category. A subject with multiple CTCAE grades for the same preferred term will be summarized under the maximum CTCAE grade recorded for the event. AE with missing CTCAE grade will be included in the 'All grades' column of the summary tables.

In AE summaries, the primary SOC will be presented alphabetically and the PT will be sorted within primary SOC in descending frequency. The sort order for the PT will be based on their frequency in patient's arm.

The following adverse event summaries will be produced;

- Overview of AEs
- AEs regardless of study treatment relationship by SOC and PT
- AEs regardless of study treatment relationship by PT
- AEs with suspected relationship to study treatment by SOC and PT
- AEs with suspected relationship to study treatment by PT
- Serious Adverse Events (SAEs) regardless of study treatment relationship by SOC and PT
- SAEs regardless of study treatment relationship by PT
- SAEs with suspected relationship to study treatment by SOC and PT
- SAEs with suspected relationship to study treatment by PT
- AEs requiring additional therapy by SOC and PT

For the legal requirements of ClinicalTrials.gov, two required tables of on-treatment AEs which are non-SAEs with an incidence greater than 5%, and on-treatment death and SAEs will be provided by SOC and PT.

If for the same patient, several consecutive AEs (regardless of study treatment relationship, seriousness and severity) occurred with the same SOC and PT:

- a single occurrence will be counted if there is \leq 1 day gap between the end date of the preceding AE and the start date of the consecutive AE
- more than one occurrence will be counted if there is $>$ 1 day gap between the end date of the preceding AE and the start date of the consecutive AE

For occurrence, the presence of at least one SAE / SAE suspected to be related to study treatment / non-SAE has to be checked in a block e.g., among AE's in a \leq 1 day gap block, if at least one SAE is occurring, then one occurrence is calculated for that SAE.

2.7.1.1 Adverse events of special interest / grouping of AEs

Adverse events of special interest are not set for $[^{68}\text{Ga}]\text{Ga}\text{-DOTA-TATE PET/CT}$.

2.7.2 Deaths

All deaths (on-treatment and post-treatment) will be summarized.

All deaths will be listed and those collected during the pre-treatment and post-treatment period will be flagged.

2.7.3 Laboratory data

Grading of laboratory values will be assigned programmatically as per NCI CTCAE version 5.0. The calculation of CTCAE grades will be based on the observed laboratory values only, clinical assessments will not be taken into account.

CTCAE Grade 0 will be assigned for all non-missing values not graded as 1 or higher. Grade 5 will not be used.

For laboratory tests where grades are not defined by CTCAE version 5.0, results will be categorized as low/normal/high based on laboratory normal ranges.

The following summaries will be generated separately for hematology, and biochemistry tests:

For laboratory tests where grades are defined by CTCAE version 5.0:

- Worst post-baseline CTCAE grade (regardless of the baseline status). Each participant will be counted only once for the worst grade observed post-baseline.
- Shift tables using CTCAE version 5.0 grades to compare baseline to the worst on-treatment value.

For laboratory tests where grades are not defined by CTCAE version 5.0:

- Shift tables using the low/normal/high/ (low and high) classification to compare baseline to the worst on-treatment value.

Listing of laboratory data will be produced with values flagged to show the corresponding CTCAE version 5.0 grades if applicable and the classifications relative to the laboratory normal ranges.

All urinalysis and coagulation data will be listed.

2.7.4 Other safety data

2.7.4.1 ECG and cardiac imaging data

Number (%) of participants with abnormality will be provided by time-point (Screening and Day1_post-injection). All ECG data will be listed.

2.7.4.2 Vital signs

Notable vital sign values in participants with non-notable values at baseline (e.g. systolic blood pressure (BP) >90 and <180 mmHg for analysis of systolic BP) will be summarized by time-point (Day1_post-injection and Safety FU (i.e. Day 8)). A listing of all vital signs' assessments will be produced, and notable values will be flagged.

Table 2-3 Notable vital sign values

Vital sign (unit)	Clinically notable criteria	
	above normal value	below normal value
Systolic blood pressure (mmHg)	≥180 with increase from baseline of ≥20	≤90 with decrease from baseline of ≥20
Diastolic blood pressure (mmHg)	≥105 with increase from baseline of ≥15	≤50 with decrease from baseline of ≥15
Pulse rate (bpm)	≥100 with increase from baseline of >25%	≤50 with decrease from baseline of >25%
Respiratory rate (breaths per minute)	> 22	<14
Body temperature (°C)	≥39.1	-

2.8 Pharmacokinetic endpoints

Descriptive summary statistics of [⁶⁸Ga]Ga-DOTA-TATE blood concentration data will be provided by participant, and visit/sampling time point, including the frequency of concentrations below the LLOQ and reported as zero.

Summary statistics will include n, mean (arithmetic and geometric), SD, CV (arithmetic and geometric), median, minimum, and maximum.

Drug concentrations below LLOQ will be treated as missing for the calculation of the geometric means and geometric CV%, and as zero for all other calculations including calculation of PK parameters.

All individual and overlaid concentration-time profiles for [⁶⁸Ga]Ga-DOTA-TATE blood concentration will also be represented graphically (including spaghetti plots and mean plots with SD) on the linear and semi-log view based on nominal time.

All individual [⁶⁸Ga]Ga-DOTA-TATE blood concentration data will be listed by time point for participants with PK concentration in the FAS.

The PAS will be used in all pharmacokinetic data analysis and PK summary statistics.

Pharmacokinetic variables:

The following pharmacokinetic parameters will be determined using the actual recorded sampling time s and non-compartmental method(s) with Phoenix WinNonlin (Version 6.4 or higher):

AUCinf, AUClast, Cmax, Tmax, T1/2, Lambda_z, CL and Vz.

In addition, the following pharmacokinetic parameters may be determined, if deemed appropriate, using the actual recorded sampling time s and two-compartmental method(s) with Phoenix WinNonlin (Version 6.4 or higher):

V1, K10, K12, K21, AUC, K10 T1/2, Alpha, Beta, Alpha T1/2, Beta T1/2, V2, CL.

Bio-fluid concentrations will be expressed in mass per volume units and, if deemed necessary, other units (e.g. radioactivity per volume). All concentrations below the limit of quantitation or missing data will be reported as such in the concentration data listings. Concentrations below the limit of quantitation will be treated as zero in summary statistics. Refer to [Section 5.7](#) for the derivation of mass-based dose and concentrations.

Pharmacokinetic parameters will be provided by participants. Descriptive statistics of all pharmacokinetic parameters will include n, arithmetic and geometric mean, median, SD, and CV, geometric CV, minimum, and maximum. Zero concentrations will not be included in the geometric mean calculation. Since Tmax is generally evaluated by a nonparametric method, median values and ranges will be given for this parameter. These summaries will be presented for PK parameters from non-compartmental method(s) and two-compartmental method(s), separately.

PK parameters data will be listed (including AUC %extrapolated) by participant and for PK parameters from non-compartmental method(s) and two-compartmental method(s), separately.

Table 2-4 Non-compartmental pharmacokinetic parameters

AUClast	The AUC from time zero to the last measurable concentration sampling time (tlast) (mass x time x volume ⁻¹)
AUCinf	The AUC from time zero to infinity (mass x time x volume ⁻¹)
Cmax	The maximum (peak) observed plasma, blood, serum, or other body fluid drug concentration after single dose administration (mass x volume ⁻¹)
Tmax	The time to reach maximum (peak) plasma, blood, serum, or other body fluid drug concentration after single dose administration (time)
Lambda_z	Smallest (slowest) disposition (hybrid) rate constant (time ⁻¹) may also be used for terminal elimination rate constant (time ⁻¹)
T1/2	The elimination half-life associated with the terminal slope (λ_z) of a semi logarithmic concentration-time curve (time). Use qualifier for other half-lives
CL	The total body clearance of drug from the plasma (volume x time ⁻¹)
Vz	The apparent volume of distribution during terminal phase (associated with λ_z) (volume)

2.9 PD and PK/PD analyses

Not applicable.

2.10 Patient-reported outcomes

Not applicable.

2.11 Biomarkers

Not applicable.

—

For more information, contact the Office of the Vice President for Research and Economic Development at [contact] or [contact].

10.1007/s00339-007-0332-2

10. *Journal of the American Statistical Association*, 1980, 75, 338-342.

[figure not shown]
© 2019 Pearson Education, Inc.

10. *Journal of the American Statistical Association*, 1980, 75, 338-342.

© 2010 Pearson Education, Inc. All Rights Reserved. May not be reproduced, in whole or in part, without permission of the publisher.

10.1007/s00332-010-9000-0

10.1007/s00332-017-9170-2

2.13 Interim analysis

Not applicable.

3 Sample size calculation

The primary endpoints of the study are subject-level sensitivity and specificity based on central read.

The sample size was calculated based on the following assumptions for primary endpoints.

- Assumptions for subject-level sensitivity: expected sensitivity of 90% and threshold of 70%
- Assumptions for subject-level specificity: expected specificity of 90% and threshold of 60%

The expected sensitivity and specificity are respectively set as 90% based on the systematic review publication on [⁶⁸Ga]Ga-DOTA-TATE (Deppen et al 2016). The thresholds of 70% for sensitivity and 60% for specificity are set by referring to phase III study of [64Cu]Cu-DOTA-TATE (Delpassand et al 2020) and the thresholds will be considered reasonable to show clinical relevant diagnostic performance in this study. For sensitivity, 47 participants with positive result in CIM are required to reject the null hypothesis of sensitivity $\leq 70\%$ with 1-sided alpha level of 2.5% and $\geq 90\%$ power with exact binomial test. For specificity, 23 participants with negative result in CIM are required to reject the null hypothesis of specificity $\leq 60\%$ with 1-sided alpha level of 2.5% and $\geq 90\%$ power with exact binomial test. Therefore, 47 confirmed/suspected NEN patients (expected to be positive in CIM) and 23 HVs (negative in CIM) are required. As a result, 70 participants are required as Efficacy Analysis Set (EFF) in total. The study enrollment will continue until 70 participants in the EFF.

Table 3-1 Sensitivity of power to changes in number of participants

N_Sensitivity	Power for Sensitivity	N_Specificity	Power for Specificity
42	87.9%	28	94.5%
43	86.7%	27	95.3%
44	85.4%	26	96.0%
45	92.4%	25	90.2%
46	91.6%	24	91.5%
47	90.7%	23	92.7%

The N for sensitivity is based on NEN patients with positive result in CIM. The N for specificity is based on NEN patients with negative result in CIM in addition to HVs (i.e., some NEN patients out of 47 patients will be used for specificity estimation instead of sensitivity if the result in CIM is negative).

4 Change to protocol specified analyses

Analyses related to AESI are not planned since AESI are not set for [⁶⁸Ga]Ga-DOTA-TATE PET/CT ([Section 2.7.1.1](#)).

Supplementary analysis for the primary endpoints which excludes participants with readable but not optimal [⁶⁸Ga]Ga-DOTA-TATE PET/CT imaging judged by central read is added since the readability categories was updated ([Section 2.5.6](#)).

5 Appendix

5.1 Imputation rules

5.1.1 Study drug

The complete date of dose administration is required for this study. Completely or partially missing date will not be imputed and should be considered as a data issue and the statistician should contact the data manager of the study.

5.1.2 AE, ConMeds and safety assessment date imputation

Table 5-1 Imputation of start dates (AE, CM) and assessments (LB, EG, VS)

Missing Element	Rule
day, month, and year	
No imputation will be done for completely missing dates
day, month	
If available year = year of study treatment start date, then
If stop date contains a full date and stop date is earlier than date of dose administration, then set start date = 01JanYYYYElse set start date = date of dose administration.If available year > year of date of dose administration, then 01JanYYYYIf available year < year of date of dose administration, then 01JulYYYY
day	
If available month and year = month and year of date of dose administration, then
If stop date contains a full date and stop date is earlier than date of dose administration, then set start date= 01MONYYYY.Else set start date = date of dose administration.If available month and year > month and year date of dose administration, then 01MONYYYYIf available month and year < month year of date of dose administration, then 15MONYYYY

Table 5-2 Imputation of end dates (AE, CM)

Missing Element	Rule (*=date of dose administration plus 8 days not > (death date, database lock date, withdrawal of consent date))
day, month, and year	
Completely missing end dates (incl. ongoing events) will be imputed by the end date of the on-treatment period*
day, month	
If partial end date contains year only, set end date = earliest of 31DecYYYY or end date of the on-treatment period *
day	
If partial end date contains month and year, set end date = earliest of last day of the month or end date of the on-treatment period*

Any AEs and ConMeds with partial/missing dates will be displayed as such in the data listings.

Any AEs and ConMeds which are continuing as per data database lock will be shown as 'ongoing' rather than the end date provided.

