2.1.1 General definitions

Study treatment/ drug

Study treatment/ drug is [⁶⁸Ga]Ga-DOTA-TATE administered intravenously at a dose of 2 MBq/kg (0.054 mCi/kg) of body weight up to a total maximum dose of 200 MBq (5.4 mCi) even if no [⁶⁸Ga]Ga-DOTA-TATE PET/CT scan was acquired.

Study day

The study day describes the day of the event or assessment date, relative to the reference start date.

The study day is defined as:

- The date of the event (visit date, onset date of an event, assessment date etc.) – reference start date + 1 if event is on or after the reference start date;
- The date of the event (visit date, onset date of an event, assessment date etc.) – reference start date if event precedes the reference start date.

The reference date for all assessments is the start of study treatment.

The study day will be displayed in the data listings. If an event starts before the reference start date, the study day displayed on the listing will be negative.

Time unit

A year length is defined as 365.25 days. A month length is 30.4375 days (365.25/12). If duration is reported in months, duration in days will be divided by 30.4375. If duration is reported in years, duration in days will be divided by 365.25.

Baseline

The last available assessment including unscheduled assessments before injection of study drug is taken as “baseline” value or “baseline” assessment.

If participants have no value as defined above, the baseline result will be missing.

On-treatment assessment/event and observation periods

The overall observation period will be divided into three mutually exclusive segments:

1. Pre-treatment period: from day of participant’s informed consent to the day before dosing of investigational drug.
2. On-treatment period: from day of dosing of investigational drug to 8 days after dosing of investigational drug. (i.e. Day 1 – Day 9)
3. Post-treatment period: starting 9 days after dosing of investigational drug. (i.e. start from Day 10)

If dates are incomplete in a way that clear assignment to pre-, on-, post-treatment period cannot be made, then the respective data will be assigned to the on-treatment period.

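### SAP Table 5-1 dates a screening laboratory sample with a missing day in the dosing month to the injection day, so a pre-dose value can enter the on-treatment laboratory tables

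*SAP*

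**What the plan says.** The title of SAP Table 5-1 (section 5.1.2) sets its scope: "Imputation of start dates (AE, CM) and assessments (LB, EG, VS"). LB, EG and VS are laboratory, ECG and vital-sign records.

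For a missing day, the first branch opens with "If available month and year = month and year of date of dose administration, then" and has two outcomes:
- the exception: "If stop date contains a full date and stop date is earlier than date of dose administration, then set start date= 01MONYYYY";
- the default: "Else set start date = date of dose administration".

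A record from an earlier month is set to the 15th of that month, and one from a later month to the 1st. When day and month are both missing, the layout is the same with the year in place of the month. A record from the dosing year takes the dose date unless a full stop date precedes dosing, and one from an earlier year is set to 1 July of that year.

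SAP 2.1.1 defines the periods by day: "On-treatment period: from day of dosing of investigational drug to 8 days after dosing of investigational drug. (i.e. Day 1 – Day 9"). If an incomplete date prevents clear assignment to a period, "then the respective data will be assigned to the on-treatment period". Baseline is tied to the injection: "The last available assessment including unscheduled assessments before injection of study drug is taken as" baseline.

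For haematology and biochemistry, SAP 2.7.3 tabulates the worst post-baseline CTCAE grade, and shift tables that "compare baseline to the worst on-treatment value". Protocol Table 1-2 schedules these tests at screening, before injection on Day 1, and at the safety follow-up on Day 8 ±1.

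**The concern.** Table 5-1 is built for records with a duration. When an AE's onset is unclear, counting it as on-treatment is cautious, and the stop date rescues an event that clearly ended before dosing. A blood sample has one date and no stop date, so the rescue cannot operate. A sample in the dosing month always takes the default.

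A scheduled sample is also unlike an AE in that its visit label normally says on which side of the injection it lies. Table 5-1 makes no use of that label. Neighbouring rules are more careful. SAP 5.1.1 treats an incomplete dose date as a data issue and does not impute it. SAP 5.1.2.1 caps imputed diagnosis and relapse dates at informed consent.

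At stake are the laboratory safety tables. An abnormality present before the tracer was given could be shown as arising after it, in small groups with one scheduled post-injection sample per person.

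**Working it through.** The documents state no figure on this point, so there is none to reproduce. The check applies the rule literally.

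**1. Single cases, day missing, no stop date**
- Dosing 28 March 2024, true screening date 10 March. Same month, so the imputed date is 28 March, which is Day 1 and on-treatment. This is wrong.
- Dosing 10 March 2024, true screening date 20 February. Earlier month, so the imputed date is 15 February, which is Day −24 and pre-treatment. The period is right.

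**2. Share of missing-day screening samples sent to Day 1**

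Inputs are the screening window of Day −35 to −1 (Protocol Table 1-2) and, as an assumption, dosing dates and screening lags spread evenly over 2021–2024. Screening at lag L days falls in the dosing month when the dosing day-of-month exceeds L. A month of m days therefore contributes (m−1) + (m−2) + … + 1 = m(m−1)/2 pairs.

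| Month length | Months in 4 years | Pairs each | Total |
|---|---|---|---|
| 31 | 28 | 465 | 13,020 |
| 30 | 16 | 435 | 6,960 |
| 29 | 1 | 406 | 406 |
| 28 | 3 | 378 | 1,134 |
| All | 48 | | 21,520 |

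All pairs: 1,461 days × 35 lags = 51,135. The share sent to Day 1 is 21,520 / 51,135 = 42.1%, and 57.9% stay pre-treatment.

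The share depends strongly on when screening is done: 86.9% for Day −7 to −1, 75.4% for −14 to −1, 19.9% for −35 to −15, and 1.9% for −35 to −28.

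With only the year known, the sample misses the dosing year when the dosing day-of-year is at most L. That is 1 + 2 + … + 35 = 630 pairs a year, or 2,520 in four years. The share sent to Day 1 is (51,135 − 2,520) / 51,135 = 95.1%.

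These are shares of records with incomplete dates, not of participants.

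**3. Day 8 ±1 samples, day missing**

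Some 77.0% are redated to Day 1. The rest are set to the 1st of the next month, which is Day 2 to Day 9. All remain on-treatment, which is their true period.

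**4. Effect on the shift table**

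Let the grades be s at screening, b before injection on Day 1 and f at follow-up. The correct cell is (b, f). If the redated screening value is counted, the cell is (b, max(s, f)). It changes only if s > f. Baseline stays at b, because the pre-injection sample is still available.

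**5. Size per record**

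One healthy volunteer is 1/23 = 4.3 percentage points, and one patient is 1/47 = 2.1 points. Both use planned numbers.

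**The case against.** The strongest reply is that Table 5-1 only fills a date field and nowhere tells the programmer to ignore visit labels. Baseline is defined by the injection, not by the calendar day. Since the pre-injection sample is itself taken on Day 1, time-point information is needed for every participant, even with complete dates. A programmer who uses the labels would never count a screening sample as on-treatment. This stands as a reason to expect the error to be avoidable in practice. It does not remove the defect: the period definition is by day, the table includes assessments expressly, and no sentence gives the label precedence.

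The reply also rightly limits the reach. Dated visit procedures are covered by validation checks and queries for missing values (Protocol 10.1.5.1 and 10.1.5.2), so incomplete dates should be rare. An unknown month is less plausible still for a sample within 35 days of dosing.

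A reader might infer more than the documents support:
- **That every missing-day screening sample becomes on-treatment.** The same-month condition excludes 57.9% under the even-spread assumption.
- **That Day 8 samples are misclassified or displace baseline.** Their period stays correct. Treating a follow-up value as baseline would contradict the before-injection definition.
- **That ECG and vital-sign tables are corrupted.** SAP 2.7.4.1 and 2.7.4.2 summarise by named time point. No ECG change-from-baseline table is planned, and vital signs keep a Day 1 pre-injection reading as baseline for Table 2-3.
- **That each misdated record decides a participant's row.** It does so only when its grade is the worst.

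**Conclusion.** The point holds as a defect in the written rule, limited to the haematology and biochemistry tables of SAP 2.7.3. A screening sample with a missing day in the dosing month, or with only the dosing year known, is placed on Day 1 by a rule whose one exception cannot apply to it. Its grade can then be reported as on-treatment if it exceeds the follow-up grade.

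The per-record figures of 4.3 and 2.1 points are upper bounds. They assume the redated value is the worst one and the safety groups have the planned 23 and 47 participants. The 42.1% and 95.1% shares rest on evenly spread dosing and screening dates. The documents give no frequency of incomplete assessment dates, so the expected number of affected cells cannot be stated, but it should be small. The co-primary sensitivity and specificity analyses do not use these dates. This is a minor correction, worth making because it is specific and cheap.

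**What to change.** Remove LB, EG and VS from the scope of Table 5-1, or add one sentence saying that for assessments the recorded visit or time point prevails over any imputed date. In either case, assign baseline and observation period for laboratory, ECG and vital-sign records from the recorded visit or time point. Use the on-treatment default of SAP 2.1.1 for an assessment only when no visit or time point is recorded. Leave the rule unchanged for AEs and concomitant medications.

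The cost is a short SAP wording change and a small change to the derivation program. No new data are needed.
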